2.5.4 Windows for time points

Laboratory data

A protocol planned laboratory test is considered to have occurred during a cycle if the date of sampling is after ($>$) the first day of the cycle, but prior to or equal (\leq) to the first day of the next cycle. For unscheduled tests, a test is considered to have occurred during a cycle if the date of sampling is equal to or after (\geq) the first day of the cycle, but prior ($<$) to the first day of the next cycle.

2.5.5 Unscheduled visits

Unscheduled visit measurements of laboratory data, vital signs and ECG will be used for computation of worst values and/or grades on treatment. Unscheduled visits prior to first administration will be also used for computation of baseline except if they are not collected on the day of first administration.

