- g Vital Signs: Vital signs including blood pressure, heart rate, temperature, and respiration rate are required at Screening. The measurements will also be performed at the EOT visit, and post treatment follow up visits at 60 and 90 days after last treatment. For all patients, vital signs should be obtained prior to the start of each isatuximab infusion, 1 hour after the start of the infusion, at the end of infusion, and if clinically indicated during the infusion.
- h 12-Lead ECG: Single (not triplet). To be performed at Screening and then as clinically indicated.
- i Pregnancy Test: Women of child bearing potential must have a negative serum pregnancy test result within 7 days prior to first IMP administration. A pregnancy test (serum or urine) is to be done on Day 1 of each cycle prior to the study treatment, at the EOT visit, and every 30 (± 7) days until 6 months after the last dose of study treatment.
- **Blood Chemistry:** To be done at Screening, then prior to premedication and IMP administration, at the EOT visit, during follow-up and as clinically indicated. Biochemistry should be performed every 7 days in case of Grade 3/4 abnormalities. Blood chemistry includes: AST, ALT, bilirubin (total and direct), ALP, LDH, sodium, potassium, chloride, bicarbonate/carbon dioxide, calcium, magnesium, phosphate, uric acid, urea or BUN, serum creatinine, eGFR (MDRD formula; Appendix H), glucose (fasting), albumin and total protein. TSH will be assessed at baseline, every second cycle, EOT, during follow-up visits (60 and 90 days after last treatment); free T4 will be assessed if TSH is outside of the normal range.
- k Blood chemistry, hematology, PSA and urinalysis assessments are not required to be repeated prior to Cycle 1 Day 1 if the screening laboratory assessments were performed within 3 days prior to first IMP administration.
- Hematology: To be done at Screening, then prior to premedication and IMP administration, at the EOT visit, during follow-up and as clinically indicated. Hematology includes: Hemoglobin, hematocrit, RBC, WBC with differential, and platelet counts. If Grade 4 neutropenia, assess ANC every 2 to 3 days until ANC ≥0.5 × 10^9/L and at least weekly thereafter until ANC ≥1.0 × 10^9/L. Blood group card to be obtained before study entry.
- m Coagulation: To be done at Screening and then as clinically indicated. Coagulation includes: prothrombin time or INR and activated PTT.

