#### 13.4 STATISTICAL METHODS

A list of study endpoints and their definitions are provided in Section 9.6.

Unless otherwise specified, analyses will be descriptive and performed based on the all-treated population. The baseline for a given parameter is defined as the last assessment for this parameter before first administration of study treatments unless otherwise noted.

Data from mCRPC and NSCLC cohorts in the Phase 2 part will be analyzed and reported separately by cohort. Data from the cohort A-2 cross-over part will be summarized separately unless otherwise noted.

Continuous data will be summarized using number of available data, mean, standard deviation, median, minimum and maximum for each dose level (if applicable). Categorical and ordinal data will be summarized using number and percentage of patients in each dose level (if applicable). Summary tables will be presented by dose level and overall (if applicable), unless otherwise noted.

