#### 13.4.5.4 Clinical laboratory evaluations

Clinical laboratory values will be analyzed after conversion into standard international units. International units will be used in all listings and tables. Complete blood count and serum chemistry results will be graded according to NCI-CTCAE version 4.03, when applicable. For patients with multiple occurrences of the same laboratory variable during the TEAE period, the maximum grade (worst) per patient will be used. The denominator used for percentage calculation is the number of patients with at least 1 evaluation of the laboratory test during the considered observation period.

The number and proportion of patients with abnormal laboratory tests at baseline (ie, last assessment before the first dose of study treatments administration) will be presented for all grades together and each grade separately. Similar tables showing abnormalities during the TEAE period will be provided.

When the NCI-CTCAE version 4.03 scale is not applicable, the number of patients with a laboratory abnormality out-of-normal laboratory range value will be displayed.

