2.1 ANALYSIS ENDPOINTS

2.1.1 Demographic and baseline characteristics

The baseline value is defined as the last assessment for this parameter before first administration of study treatments unless otherwise noted.

All baseline safety and efficacy parameters (apart from those listed below) will be presented along with summary statistics in the safety and efficacy sections ([Section 2.4.5](#) and [Section 2.4.6](#)).

Demographic characteristics

Demographic variables include race (American Indian or Alaska Native, Asian, Black or African American, Native Hawaiian or Other Pacific Islander, White, Not reported, Unknown), ethnicity (Hispanic or Latino, Not Hispanic or Latino, Not reported, Unknown), age in years, weight (kg), height (cm) and eastern cooperative oncology group (ECOG) performance status at baseline.

Medical or surgical history

Medical or surgical history includes relevant history of previous or associated pathologies other than the tumor.

This information will be coded using the version of Medical Dictionary for Regulatory Activities (MedDRA) currently in effect at Sanofi at the time of database lock.

Disease characteristics at diagnosis

The following disease characteristics at initial diagnosis will be described:

- Time from initial diagnosis to first study treatment administration (in years)
- Histology (diagnosis as collected in electronic case report form (eCRF))
- Disease Location
- Histopathology type (as collected in eCRF)

- Stage of the disease (as collected in eCRF)
- Gleason Score (for patients with mCRPC)

Disease characteristics at study entry - mCRPC

The following disease characteristics at study entry will be described:

- Disease extent (metastatic, Loco Regional Recurrence, Primary, locally advanced)
- Criteria for progression (prostate-specific antigen (PSA), soft tissue, bone metastasis)
- Baseline PSA

Disease characteristics at study entry - NSCLC

Disease extent (metastatic, Loco Regional Recurrence, Primary, locally advanced) will be summarized.

Prior anticancer therapies

Prior anti-cancer treatments are collected by regimen in the eCRF. The following variables will be summarized:

- Prior chemotherapy (by category: 0, 1, 2, 3 or more regimens): Number (%) of patients who received Taxane chemotherapy will be summarized for mCRPC cohorts
- Number of prior regimens (by category: 1, 2, 3, >3)
- Prior radiation therapy: number (%) of patients with any prior radiotherapy related to mCRPC or NSCLC by intent

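### SAP 2.5.5 keeps an unscheduled pre-dose laboratory value out of baseline unless it was drawn on the dosing day, which contradicts protocol 13.4.5.4 (minor)

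*SAP*

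**What the plan says.** Four places set the baseline rule.

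- **Protocol 13.4, general rule:** "The baseline for a given parameter is defined as the last assessment for this parameter before first administration of study treatments unless otherwise noted".
- **Protocol 13.4.5.4, laboratory data:** baseline is the "last assessment before the first dose of study treatments administration". No exception clause is attached.
- **SAP 2.1.1, general rule:** "The baseline value is defined as the last assessment for this parameter before first administration of study treatments unless otherwise noted".
- **SAP 2.5.5, unscheduled visits:** "Unscheduled visit measurements of laboratory data, vital signs and ECG will be used for computation of worst values" and grades on treatment. Pre-dose unscheduled visits "will be also used for computation of baseline except if they are not collected on the day of first administration".

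SAP 1.5, the section for changes to the protocol's statistical section, records none. SAP 2.1.4.5 treats laboratory values from the day of first infusion as part of baseline. SAP 2.4.6.4 plans a count of patients with abnormal laboratory tests at baseline and during treatment, by grade.

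**The concern.** The double negative in SAP 2.5.5 means that an unscheduled value from any day before the dosing day can never be baseline, even when it is the most recent value available. Neither the protocol's laboratory rule nor SAP 2.1.1 distinguishes scheduled from unscheduled visits. A programmer who follows 2.5.5 will therefore derive a different laboratory baseline from the one the protocol defines, and nothing in the SAP flags the change.

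The same paragraph lets unscheduled values set the worst on-treatment grade. An unscheduled result can thus worsen the on-treatment column of the laboratory table, but before the dosing day it cannot update the baseline column. At stake is whether that baseline column describes patients as they were when treatment started.

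**Working it through.** There is no figure in the plan to reproduce. The check compares the two rules on the visit schedule. The windows come from the documents; the visit days are illustrative.

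**Inputs**
- Pretreatment examinations: within 28 days before first dose (protocol 12.2).
- Coagulation: at screening, then only as clinically indicated (protocol 1.3, footnote m). No Cycle 1 Day 1 test is scheduled.
- Chemistry, hematology and urinalysis: scheduled at screening and on Cycle 1 Day 1 before dosing. Footnote k says they "are not required to be repeated prior to Cycle 1 Day 1 if the screening laboratory assessments were performed within 3 days" before first dose.
- Vital signs: required before the start of each isatuximab infusion (footnote g); footnote k does not waive them.
- ECG: scheduled at screening only (footnote h); SAP 2.4.6.6 plans a listing and no summary.

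**Formula:** extra age of the SAP baseline = (days from the value kept by SAP 2.5.5 to first dose) − (days from the last pre-dose value to first dose).

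**Cases**
1. *Coagulation.* Screening Day -28, unscheduled retest Day -2. The protocol baseline is Day -2 and the SAP baseline is Day -28: 28 − 2 = 26 days older. With the retest on Day -1, the limit is 28 − 1 = 27 days.
2. *Cycle 1 Day 1 test done.* It follows the retest, and both rules select it: 0 days.
3. *Cycle 1 Day 1 test missed.* The SAP falls back to the scheduled screening value, which may be up to 28 days old. With the days of case 1, the difference is again 26 days.
4. *Cycle 1 Day 1 test waived because the screening test was recent.* Screening is at the earliest on Day -3. With an unscheduled retest on Day -1, the difference is at most 3 − 1 = 2 days.
5. *Waiver supported by a retest that the database codes as unscheduled (assumption).* Screening Day -14, retest Day -2: 14 − 2 = 12 days older. The documents do not say that such a retest would be coded this way.

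**Where the difference surfaces.** SAP 2.1.4.5 includes coagulation among the hematology parameters, so case 1 reaches the baseline abnormality table of SAP 2.4.6.4. Worst on-treatment grades come from values after dosing starts and do not depend on which pre-dose value is baseline.

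**The case against.** The strongest defence is that the general definitions in protocol 13.4 and SAP 2.1.1 apply unless something else is noted, and SAP 2.5.5 may be that note. This is a fair answer for vital signs and ECG. It fails for laboratory data, because protocol 13.4.5.4 has no such clause.

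A second defence is that the double negative is a drafting slip. SAP 2.5.4 assigns an unscheduled test on the first day of a cycle to that cycle, which would fit an intention to exclude dosing-day values, the reverse of the literal text. That is plausible, but the documents do not settle it, and a sentence that may say the opposite of what was meant still needs correcting.

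Several stronger readings are tempting but unsupported:

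- *A patient who failed E20 and passed on retest keeps the failing value as baseline.* Take an illustrative neutrophil count of 1.2 × 10^9/L on Day -14 and 1.7 on Day -2, with no Cycle 1 Day 1 test. The retest must count as a screening assessment to trigger the waiver, yet as unscheduled to be dropped. If it is screening data, 2.5.5 does not remove it. If it is unscheduled, the waiver does not apply, and the required Cycle 1 Day 1 test becomes baseline under both rules. E20 is judged at the Screening visit and one re-screening is allowed, so such a retest fits naturally as screening data.
- *On-treatment values will look unchanged or improved.* SAP 2.4.6.4 plans no laboratory shift or change-from-baseline analysis.
- *Baseline abnormalities will be overstated.* That assumes retests follow abnormal first results. The documents do not say why retests are done, so the direction is open.
- *Vital-sign change criteria are distorted.* A reading before the first isatuximab infusion is mandatory, and SAP 2.1.4.6 counts dosing-day readings as baseline. An older value could enter only if that required reading were missed.
- *The PSA part of the primary endpoint is affected.* SAP 2.5.5 does not name PSA, the safety laboratory list in SAP 2.1.4.5 omits it, and protocol Appendix A, Table 9 sets the PSA baseline at Cycle 1 Day 1.

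**Conclusion.** The contradiction is real for laboratory data, undeclared, and narrow. It rests on the literal reading of SAP 2.5.5 and changes a result only when an unscheduled value taken before the dosing day is the last pre-dose value. Coagulation is the main exposure, with a baseline up to 27 days older than the protocol's. Missed Cycle 1 Day 1 tests come next. Properly waived tests differ by at most 2 days, and the larger difference in case 5 depends on a coding assumption.

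In practice the consequence is confined to cells of a descriptive safety table. How many patients would be affected cannot be estimated, because the documents give no rate of pre-dose retesting and no rule for coding retests. Severity: minor.

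**What to change.** Replace the exception in SAP 2.5.5 with: *Baseline is the last non-missing value before the first study treatment administration, from scheduled or unscheduled visits.* This agrees with protocol 13.4.5.4 and SAP 2.1.1.

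Align SAP 2.5.4 at the same time. As it stands, an unscheduled sample drawn on Day 1 before dosing would fall in Cycle 1. State that such a sample is a baseline value and not a Cycle 1 value.

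If the sponsor does want to restrict unscheduled values, it should declare the departure in SAP 1.5 and give the reason.

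The cost is one replacement sentence, a short clarification in 2.5.4, and the matching changes to the baseline and cycle-assignment programming. No new data are needed.

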2.5.6 Pooling of centers for statistical analyses

Data from all sites will be pooled together for analyses.

2.5.7 Statistical technical issues

Not applicable

3 INTERIM ANALYSIS (IA)

An IA will be performed for each cohort after the first 23 patients for mCRPC cohorts or the first 20 patients for NSCLC cohorts in the Phase 2 part have completed 6 cycles. The interim analysis may be conducted earlier if the required number of responders proceeding to Phase 2 Stage 2 is achieved.

The analysis will include the following parameters/analyses (defined in [Section 2.1](#)): response rate, demographics and baseline characteristics, prior or concomitant medication, AEs (TEAE, death, SAE, TEAE leading to discontinuation, IAR, AESI), and laboratory variables (abnormality of hematological and chemistry test). If needed, more data will be analyzed to inform the futility decision including additional efficacy, PK, and biomarker.

4 DATABASE LOCK

The database will be locked when clinical review of the database has been completed and all critical queries have been resolved.

5 SOFTWARE DOCUMENTATION

All summaries and statistical analyses will be generated using SAS® version 9.4 or higher.

7 LIST OF APPENDICES

Appendix A Generic ranges for hematological and biochemistry parameters

Table 6 - Generic ranges for hematological parameters

Test	Gender	Unit	Lower/Upper limit of normal
Hemoglobin	F	g/L	120 - 160
Hemoglobin	M	g/L	135 - 175
Lymphocytes		109/L	1-2
Neutrophils		109/L	1.8 – 3.15
Platelets		109/L	150 - 350
Leukocytes		109/L	4.5 - 11
Eosinophils		109/L	0 – 0.4
Basophils		109/L	0 – 0.15
Monocytes		109/L	0.18 – 0.5
Hematocrit	M	Ratio	0.41 -0.53
Hematocrit	F	Ratio	0.36 – 0.46
Erythrocytes	F	1012/L	4 – 5.2
Erythrocytes	M	1012/L	4.5 -5.9
INR		ratio	0.8 -1.2

Based on Kratz et al.(4)

Table 7 - Generic ranges for biochemistry parameters

Test	Unit	Lower – Upper limit of normal
Albumin	g/L	35 - 55
BUN	mmol/L	3.6 – 7.1
Calcium	mmol/L	2.2 - 2.6
Chloride	mmol/L	80 - 115
Corrected calcium	mmol/L	2.2 – 2.6
Glucose	mmol/L	3.9 - 7
Bicarbonate (HCO ₃)	mmol/L	22 - 29
Carbon dioxide	mmol/L	21 - 30
Potassium	mmol/L	3.5 - 5
Magnesium	mmol/L	0.8 - 1.2
Sodium	mmol/L	136 - 145
Phosphate	mmol/L	1 - 1.4
Protein	g/L	55 - 80
Urea	mmol/L	3.6 - 7.1

ACT15319 16.1.9 Statistical analysis plan

ELECTRONIC SIGNATURES

Signed by	Meaning of Signature	Server Date (dd-MMM-yyyy HH:mm)
